9.2 POWER CALCULATIONS

Power calculations were estimated using the Bonferroni correction. The Bonferroni correction adjusts probability (p) values because of the increased risk of a type I error when making multiple statistical tests (in this instance, the increased risk of type I error for the multiple outcomes of PHC and MHC scores of HRQOL, as assessed by the MSQOL-54 questionnaire) (Osoba et al., 1998; Taphoorn, et al., 2005).

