9. STATISTICAL METHODS

9.1 SAMPLE SIZE ESTIMATION & JUSTIFICATION

The two primary outcome measures for this study are changes in Physical Health Composite (PHC) and Mental Health Composite (MHC) derived from the MSQOL-54. PHC and MHC are derived by combining scores of relevant subscales (Vickrey et al., 1995). For the proposed MSOC – RCT, sample sizes were calculated in order to detect a 5-point difference in the PHC and MHC scores (a minimum clinically meaningful change in these HRQOL measures, between the intervention and standard-care arms).

To further account for loss-to-follow-up from the study period, based upon MSOC - Feasibility results, we anticipated a 42% loss-to-follow-up between randomisation and follow-up at 12 months. It is likely

this level of loss-to-follow-up is an overestimate of what will be observed in the proposed MSOC – RCT due to redevelopment of the intervention based upon feasibility data, but this overestimate will account for participants in the standard-care course that request access to the MS Online Intervention course after unblinding at 12 months after participants undertake the MS Online Standard-care course.

Taking these factors into account, we estimate 1054 participants, 527 in each arm (1:1 allocation) with data at baseline and follow-up would give 80% power to detect a 5-point change in HRQOL across both PHC and MHC outcomes. This estimation of power is based on the mean PHC and MHC scores and their SD, which is the SD between groups at baseline.

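### Bonferroni is the only multiplicity method named for PHC and MHC, and no final testing rule is set; Holm would keep the same familywise error bound with modestly more power

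*Combined protocol and SAP*

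**What the plan says.** Section 9.1 names change in PHC and change in MHC as the two primary outcome measures. It claims that 527 per arm gives "80% power to detect a 5-point change in HRQOL across both PHC and MHC outcomes", allowing for 42% loss to follow-up at 12 months. Section 9.2 states "Power calculations were estimated using the Bonferroni correction" and gives the reason: "the increased risk of type I error for the multiple outcomes of PHC and MHC scores of HRQOL". It also describes the method in general terms: "The Bonferroni correction adjusts probability (p) values because of the increased risk of a type I error when making multiple statistical tests".

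Section 9.3 gives linear regression for quality of life and no multiplicity procedure. The Data Analysis text at the end of Section 12 leaves a statistical analysis plan to be developed. Alpha, sidedness and the value of the SD are not stated. On the SD, Section 9.1 says only "This estimation of power is based on the mean PHC and MHC scores and their SD, which is the SD between groups at baseline".

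**The concern.** Bonferroni holds each composite to half the familywise alpha, whatever the other one shows. Familywise control does not require that. Once one composite is significant at alpha/2, the other can be tested at full alpha without exceeding the bound. Holm's procedure does this: compare the smaller p-value with alpha/2 and, if it is significant, the larger with alpha. It holds the familywise error under any correlation, and it rejects everything Bonferroni rejects and sometimes more.

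For example, p = 0.010 for PHC and p = 0.035 for MHC establish only PHC under Bonferroni at 0.05, but both under Holm. The primary objective in the synopsis asks for improvement in both domains, so the second composite matters here. Because Section 9.2 is the only text on multiplicity, an analyst would be likely to carry Bonferroni into the final tests by default.

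**Working it through.** **Inputs from the plan:** difference 5 points; power 80%; 527 per arm; 42% loss; family of two tests (Sections 9.1 and 9.2).

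**Assumed, because not stated:** two-sided familywise alpha 0.05, so 0.025 per composite under Bonferroni (critical value 2.2414; at 0.05 it is 1.9600); correlation between the two test statistics 0.3 to 0.8.

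**1. Reproducing the sample size.** The SD has to be back-solved. With SD 20:

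- n per arm = 2 × (20/5)² × (2.2414 + 0.8416)² = 304.2, so 305.
- 305/0.58 = 525.9, so 526, against 527 stated.

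The match is not unique. SD 22 at unadjusted alpha 0.05 gives 2 × (22/5)² × (1.9600 + 0.8416)² = 303.9, so 304, and 304/0.58 = 524.1, so 525. Section 9.2 says Bonferroni was used, which favours the SD 20 reading, but the plan's figure cannot be confirmed.

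**2. Expected test statistic.** Evaluable per arm: 527 × 0.58 = 305.7, taken as 306. Mean of each test statistic: 5/(20 × √(2/306)) = 3.092. Power per composite under Bonferroni: Φ(3.092 − 2.2414) = 80.3%. The comparison below depends on SD and n only through this mean, so any pair that delivers about 80% per composite gives the same result.

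**3. Bonferroni against Holm, true effect of 5 points on both.** Let Z1 and Z2 be bivariate normal with this mean.

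- Both significant, Bonferroni: P(Z1 > 2.2414 and Z2 > 2.2414).
- Both significant, Holm: 2 × P(Z1 > 2.2414 and Z2 > 1.9600) − P(Z1 > 2.2414 and Z2 > 2.2414).
- Per composite, Holm: the Bonferroni power plus P(Z1 > 2.2414 and 1.9600 < Z2 < 2.2414).

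| Correlation | Per composite: Bonferroni / Holm | Both: Bonferroni / Holm | At least one (either method) |
|---|---|---|---|
| 0.3 | 80.3% / 85.2% | 67.0% / 76.9% | 93.5% |
| 0.5 | 80.3% / 84.8% | 69.1% / 78.1% | 91.4% |
| 0.7 | 80.3% / 84.3% | 71.6% / 79.7% | 88.9% |
| 0.8 | 80.3% / 84.0% | 73.2% / 80.7% | 87.3% |

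**4. Unequal effects.** If one composite has a 5-point effect and the other 3.5 points, power for the weaker one rises from 47% to 56-57%. If only one composite responds, its power is 80.3% under Bonferroni and 80.3-80.4% under Holm (correlation 0 to 0.9).

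**5. Error rates, by simulation (2 million draws, correlation 0 to 0.9).** With no effect on either composite, the familywise error is the same for both methods: 4.9% at correlation 0, falling to 3.6% at 0.9. With an effect on one composite only, the error on the other is 2.5% under Bonferroni and 3.8-4.5% under Holm. The bound of 5% holds throughout, although the realised error is not identical.

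**6. If both composites are required.** No split is needed. At correlation 0.5, 80% power for both needs 644 randomised per arm under Bonferroni, 549 under Holm, and 542 with each composite tested at 0.05.

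**The case against.** The strongest objection is that Section 9.2 describes a power calculation and not a testing rule. That stands. A reader might infer that the plan commits to a single-step Bonferroni test. The documents do not say so: Section 9.2 sits under a power heading, its sentence on p-values describes the method in general, and Section 9.3 is silent. Sizing at alpha/2 is also a sound basis for a Holm analysis, whose first step is alpha/2. What remains is that the only method named is the less powerful one and that no rule replaces it.

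A reader might also infer that Bonferroni wastes power for no return. That is too strong. It gives simple simultaneous intervals that match its tests, which matters where the objective turns on a 5-point difference. Holm does not give these as easily: an outcome with p = 0.035 can be significant under Holm while its 97.5% interval includes zero.

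The size of the gain can be questioned too. Section 9.1 can be read as 527 per arm already with data. With SD 20 that gives about 96.5% power per composite under Bonferroni, against 98.2% at unadjusted 0.05, so Holm would gain under 2 points. But 96.5% contradicts the plan's own 80%. With 527 evaluable, 80% needs an SD of about 26.3, and the gain is then as tabulated.

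Finally, Holm over two composites does not deal with repeated assessment. Section 6.1 places the primary objective at both 12 months and 2.5 years, so the rule has to sit within whatever alpha each time point receives. It also presupposes that a claim on either composite counts. If both are required, testing each at full alpha is better than Holm.

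**Conclusion.** The point holds as a cheap improvement, not as an error in the plan. Bonferroni is valid if used. Compared with Holm it would cost about 4 to 5 percentage points of power per composite, and about 7 to 10 points in the chance that both are significant. It would cost nothing for at least one composite, and at most about 0.2 points if only one responds. These sizes rest on two-sided familywise alpha 0.05, 80% power per composite under Bonferroni, a true 5-point effect on both, and correlation 0.3 to 0.8; none of these is fully specified in the documents. That Holm is never less powerful than Bonferroni under the same familywise bound needs none of them.

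**What to change.** In Section 9.3, state alpha and sidedness and add the rule. At each time point designated primary, and within the alpha assigned to it, PHC and MHC are tested by Holm: the smaller p-value against alpha/2 and, if significant, the larger against alpha. With a single primary time point and alpha 0.05, these are 0.025 and then 0.05.

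Keep the sample size of 1054 and describe the Bonferroni calculation in Section 9.2 as a conservative planning basis. Report estimates with confidence intervals, and note that fixed 97.5% intervals may not match the Holm decision for the second composite. If success is defined as requiring both composites, say so and test each at full alpha instead.

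The cost is a few lines of text, to be settled before unblinding, with no new data or participants. The small downside is the less simple match between intervals and tests.

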Primary Objectives:	
To determine whether participants adhering to lifestyle modification recommendations outlined in the MS Online intervention course have clinically significant increased health-related quality of life (HRQOL) in both domains of physical and mental health compared with participants following recommendations of the MS Online standard-care course. These outcomes will be examined in the short-term (6 and 12 months) and in the medium-term (2.5 years).
 
That is, we aim to determine whether participants in the Online intervention course following recommended lifestyle modifications have clinically significant and material increases in Physical Health Composite (PHC) and Mental Health Composite (MHC) scores, as derived from the validated tool designed to measure HRQOL in people with MS (MSQOL-54) compared with participants following recommendations of the Online standard-care course.

Secondary Objectives	
To determine whether participants following the lifestyle modification recommendations in the Online MS intervention course have improved depression, anxiety, fatigue, disability and self-efficacy in the short-term and medium-term compared with people following recommendations of the Online MS standard-care course.

Inclusion Criteria:	
Eligible participants must:
 
 1. Be able to read, write, and speak English; 2. Be 18 years old or over; 3. Have a confirmed diagnosis of relapsing-remitting MS by a neurologist preceding recruitment; 4. Be able to access the internet and be able to view sessions.
Exclusion Criteria:	
Exclusion criteria of participants include:
 
 1. Experiencing any serious co-morbid chronic illness or neurological illness/injury other than MS that would threaten regular participation or significantly affect the outcome measures in its own right, such as motor neurone disease or stroke, as determined by the study investigators; 2. Currently participating in another study or self-management program involving modification of lifestyle.
Number of Planned Participants:	
1054 participants, 527 in each arm at 1:1 allocation (intervention and standard-care arm)

Investigational product:	
Not applicable

Safety considerations:	
Participation in the study poses no physical risk to participants as the proposed RCT involves taking part in an Online MS

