The Hospital Anxiety and Depression Scale (HADS) for the presence of and severity of anxiety and depressive symptoms. The HADS is commonly used for screening for anxiety and depression, as well as selecting and monitoring treatment and has been used to measure depression in MS (Zigmond & Snaith, 1983).

i. Patient-reported disability

The Patient-Determined Disease Steps (PDDS) is a self-reported measure of ambulatory disability. The PDDS is scored ordinally from 0 (normal) to 8 (bed bound) with detailed descriptors and definitions. It correlates well with the EDSS and moderately with the widely used Multiple Sclerosis Functional Composite and has excellent test-retest reliability. PDDS is considered a practical tool to use to assess changes in disability over time (Hohol, Orav, & Weiner, 1999). One step will be considered a clinically meaningful change in the PDDS.

j. Self-efficacy

Self-efficacy (the belief in one's ability to produce the effects or outcomes one wants) will be measured using the University of Washington Self-Efficacy (UWSE) survey, a psychometrically sound instrument that includes 6 items for measuring self-efficacy, validated in MS (Amtmann et al., 2012).

Primary intervention quantitative outcomes/endpoints:

The two primary outcome measures for this study are changes (improvements) from baseline in 1. Physical Health Composite (PHC) and 2. Mental Health Composite (MHC) derived from the MSQOL-54 in the short-term and medium-term. Differences of at least five points have previously been determined as the minimum clinically meaningful change in an HRQOL measure (Osoba, Rodrigues, Myles, Zee, & Pater, 1998; Taphoorn & Bottomley, 2005). Previous data suggests a difference of five points is achievable in a sample of people with MS (Hadgkiss, Jelinek, Taylor, et al., 2015).

Secondary intervention quantitative outcomes/endpoints:

Secondary outcomes include clinically relevant changes (improvements) in depression, anxiety fatigue, disability and self-efficacy in the short-term and medium-term.

QUALITATIVE OUTCOMES

A qualitative study using semi-structured interviews will be conducted within one month and 12 months after completing the MS Online course (the same group of people with MS will be interviewed at both time points).

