- V. Interested participants meeting the study eligibility criteria (Refer to Section 6.2 and 6.3 for eligibility criteria) after completing the eligibility questions will be emailed a participant information form and consent form. Once participants have provided their consent by ticking a box online, participants will be emailed a link to the baseline questionnaire to obtain demographic data and obtain data on lifestyle and outcome measures (Section 4.3, Table 1). Interested participants not meeting the study eligibility criteria will be excluded and notified by email that they were not eligible to participate in the study and thanking them for their interest.
- VI. Participants will be randomised to either the MS Online intervention course or the MS Online standard-care course at a ratio of 1:1 using simple randomisation. Randomisation will occur over a 2-week period after recruitment of eligible participants.
- VII. Participants will undertake the MS Online course (intervention arm or standard-care arm) over a 6-week period. Note, each arm is of comparable length and content-type (video, interviews, images, interactivity), to minimise variability in 'dose' received between intervention and standard-care groups. Both courses will follow a similar structure throughout, limiting differences in how the content of the course is presented.
- VIII. Patient-reported outcomes measures (Section 4.3, Table 1) will be determined after a period of 6 months, 12 months and 2.5 years after the completion of the MS Online course. This will involve participants from the MS Online intervention arm and the MS Online standard-care arm completing validated questionnaires online (following instructions and reminders, if necessary, from study team members). These measures will determine participants adherence to lifestyle recommendations of the Online intervention and standard course with respect to diet, exercise, omega 3 intake, vitamin D intake, meditation and sun exposure (Table 1). Health outcomes related to participant's quality of life, depression, anxiety, fatigue, disability and self-efficacy.
- IX. The primary objective of the study will be assessed at the 12-month and 2.5 year follow-up. That is, Health-related quality of life (HRQOL) calculations for Physical Health Composite

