(PHC) and Mental Health Composite (MHC) scores derived from the MSQOL-54 for participants in the intervention and standard-care arm will be calculated in the intervention and standard-care arms.

We will consider amending the RCT protocol to allow participants in the standard-care arm access to the MS Online intervention course before the end of the study (ie before the 2.5-year follow-up) in the event:

- a) clinically significant increases in either the PHC and MHC scores of MSQOL-54 (≥ 5) (Osoba et al., 1998; Taphoorn & Bottomley, 2005) from baseline are found in participants in the intervention arm at the 12-month follow-up who are *adhering to lifestyle recommendations* of the Online Lifestyle modifications course, but
- b) clinically significant improvements in either PHC or MHC are not found in participants in the standard-care arm at the 12-month follow-up.

If clinically significant improvements in either the PHC and MHC scores of MSQOL-54 are not found between baseline and 12 months in participants in the intervention arm *adhering to lifestyle recommendations* of the MS Online intervention course, the RCT will continue to as described to the 2.5 year follow-up.

If there are no amendments to the study, all participants will be notified of the study arm they were allocated to at the completion of the study. All participants in the standard-care arm will be provided with a link to access the MS Online intervention course.

- X. Qualitative interviewing consisting of semi-structured interviews by trained qualitative interviewers will be conducted on a randomly selected subset of participants (approximately 15 participants from intervention and standard-care arms, respectively) will be performed within 1 month of and 12 months after completing the MS Online course.
- XI. During enrolment in the trial, participants in both arms of the RCT will be advised to continue with normal medical treatment with their existing neurologists and healthcare providers and to continue with their usual medications, as recommended by their physicians.

Intervention group (MS Online intervention course):

Structure of delivery

In a seven-module, seven-session, self-administered program, participants in the intervention arm would be presented with an integrated lifestyle modification program including information and

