The complete patient-reported questionnaire with approximately 150 questions has been found to take approximately 60 minutes to complete. Participants will be able to login and complete this questionnaire over time. The participants will be requested to complete this questionnaire on four separate occasions (baseline, 6 months, 12 months and 2.5 years) and due to previous studies that we have performed within the Neuroepidemiology Unit utilising questionnaires of a similar length over 7.5 years ((Marck et al., 2018; Weiland et al., 2018), we do not believe the questionnaire will create an unacceptable burden on participants.

Quantitative data analysis:

We will measure adherence to lifestyle modification recommendations in people with MS enrolled in the MS Online intervention and the MS Online standard-care arm (control) using validated patient-reported questionnaires.

We will examine and compare clinical and health outcomes of depression, anxiety, fatigue, disability, self-efficacy and quality of life in people with MS in the short-term (6 months and 12 months) and medium-term (2.5 years) in people enrolled in the MS Online Intervention course arm and people enrolled in the MS Online standard-care course arm.

Statistical analyses will enable us to examine whether a causal relationship exists between lifestyle factors and clinical and health outcomes in people with MS. These analyses are anticipated to be completed within 6-12 months of collecting data for short-term and long-term analyses, respectively.

Qualitative data:

Qualitative data will comprise edited transcripts of recordings from semi-structured interviews from 15 randomly selected participants from the intervention arm and the standard-care arm carried out within one month of completing the MS Online course and 12 months after completing the MS Online course (the same people will be interviewed at both time points).

Interviews will be digitally recorded and transcribed by voice recognition software. Data will be stored in a re-identifiable format and encrypted files will be securely stored as described in Section 10.

Qualitative data collection feasibility:

The qualitative component of the MSOC – RCT is similar to the qualitative component of the MSOC – Feasibility study we performed. This interviewing technique was found to be both effective and participants reported positive feedback following interviews.

Qualitative data analysis:

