9.3 STATISTICAL METHODS TO BE UNDERTAKEN

Quantitative data analysis:

Clinically significant fatigue will be defined as a mean FSS > 5 (Krupp et al., 1989). Anxiety and depression will be defined as higher HADS (Zigmond & Snaith, 1983). The UWSE will be assessed as a continuous term and dichotomised at the median as there is no established cut off point indicating sufficient self-efficacy.

Characteristics of quality of life (QoL) will be measured by the MSQOL-54, including physical and mental health composite scores and multiple subdomains. Linear regression will be used to determine cross-sectional and prospective relationships with QoL. Characteristics of disability will be assessed using linear regression. Characteristics of dichotomous clinically significant fatigue, depression and anxiety will be assessed by log-binomial regression. Characteristics of Self-efficacy composite scores will be assessed by linear and log-binomial regression for continuous and dichotomised self-efficacy, respectively. Characteristics of perceived social support scores will be

assessed by linear regression. All models will be assessed for potential confounders and appropriate adjustments will be made in analyses.

Qualitative data analysis:

Audio recordings will be transcribed for analysis and stored within Nvivo Software (www.qsrinternational.com) to enable data management. Data analysis will be conducted within a qualitative paradigm using reflexive thematic analysis (Braun 2014). Reflexive thematic analysis is considered the most appropriate analytic process due its lack of grounding in a particular philosophy (Braun 2006), and as a method suitable to exploring people's experiences, views and perceptions (Braun 2014) and its allowing expression of results in a way accessible to those in the wider community. Reflexive thematic analysis also emphasises the importance of the researcher being deeply involved in the research. Data will be analysed by the process of data familiarisation, coding, and theme development and refining. Data extracts (quotes) will illustrate themes.

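### Bonferroni in 9.2 covers PHC and MHC only, while the primary time points conflict between sections and no success rule is stated; separately, 9.1 misdescribes what 527 per arm means

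*Combined protocol and SAP*

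**What the plan says.** **Correction.** Section 9.2 says the power calculation used Bonferroni because of "the increased risk of type I error for the multiple outcomes of PHC and MHC scores of HRQOL". No other source of multiplicity is mentioned, and no alpha or sidedness is given.

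**Time points.** Three places differ:
- Section 6.1, item IX: "The primary objective of the study will be assessed at the 12-month and 2.5 year follow-up".
- Synopsis, primary objectives: "These outcomes will be examined in the short-term (6 and 12 months) and in the medium-term (2.5 years").
- Section 5.3, primary endpoints: changes in PHC and MHC "derived from the MSQOL-54 in the short-term and medium-term", with no months attached.

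**Success rule.** The synopsis aims to show that participants "have clinically significant increased health-related quality of life (HRQOL) in both domains of physical and mental health". The amendment trigger in 6.1 item IX is worded in terms of either composite. No section says which rule decides the trial.

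**Analysis.** Section 9.3 offers "Linear regression will be used to determine cross-sectional and prospective relationships with QoL" and names no primary time point, alpha or correction.

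**Timing.** Item IX reads the 12-month change by arm to decide whether to consider an amendment. If the intervention arm shows no clinically significant improvement, "the RCT will continue to as described to the 2.5 year follow-up". On the schedule, "These analyses are anticipated to be completed within 6-12 months of collecting data for short-term and long-term analyses, respectively". The closing data-analysis paragraph of section 12 lists an SAP as still to be developed.

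**Sample size.** Section 9.1 attaches 80% power to 527 per arm having baseline and follow-up data. The synopsis gives 527 per arm as the planned number. Section 8.3 says withdrawals are not replaced and that the sample size already allows for 42% loss.

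**The concern.** Two tests at half the overall alpha control error for two tests. Item IX implies four comparisons (two composites at two times), and the synopsis six if every examination is a test. If any one of them could carry the primary claim, the correction in 9.2 falls short. Because 9.2 concerns power and 9.3 is silent, even the PHC/MHC correction is not carried into the analysis.

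Timing makes this matter. Results by arm are read at 12 months and the trial may then run on to 2.5 years. If the confirmatory time point and the success rule are still open at that stage, they could be chosen with the 12-month result known. Blinding the analysts to allocation (6.3) does not settle which result counts.

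The 9.1 sentence is a separate matter: read literally, it makes 527 the analysed number, which conflicts with the synopsis and 8.3.

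**Working it through.** **1. The plan's own figure.** Stated inputs: difference 5 points, power 80%, Bonferroni for two outcomes, 42% loss, 527 per arm. SD and alpha are not given, so 527 cannot be reproduced from stated inputs alone. Use n = 2(z_α + z_β)²·SD²/5² per arm, then divide by 0.58.
- Assumed SD 20, two-sided 0.025: 2(2.241 + 0.842)² × 400/25 = 304.2, so 305 analysed; 305/0.58 = 525.9, so 526 randomised. The t-test version gives 305.4 and 526.6, which rounds up to 527.
- Assumed SD 22, two-sided 0.05: 304 analysed and 525 randomised. The back-solution is therefore not unique.
- If 527 were the analysed number, the SD would be 26.3 and 527/0.58 = 909 per arm would have to be randomised. No passage plans that.

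The figures fit 527 as the number randomised: 527 × 0.58 = 305.7, about 306 per arm with 12-month data.

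**2. Error under an *either composite, any time point* rule.** Assumptions: overall two-sided 0.05, 0.025 per test, correlation 0.3–0.7 over time and 0.5–0.7 between composites (the two multiplied across time and composite). Simulation used 2,000,000 draws of correlated z-statistics.

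| Time points | Tests | Bonferroni bound | Independent tests | Simulated |
|---|---|---|---|---|
| 1 | 2 | 5.0% | 4.9% | 4.3–4.6% |
| 2 | 4 | 10.0% | 1 − 0.975⁴ = 9.6% | 7.3–8.9% |
| 3 | 6 | 15.0% | 1 − 0.975⁶ = 14.1% | 9.6–12.8% |

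**3. Error under a *both composites* rule, still at 0.025 per test.**
- No effect on either composite, two time points: about 0.6–1.4% if both must succeed at the same time point, and 0.7–1.5% if they may succeed at different ones.
- One composite truly improved, so that only the other can be a false positive: at most 2 × 0.025 = 5% with two time points and 3 × 0.025 = 7.5% with three.

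The 5% bound depends on keeping 0.025 per test. At an unsplit 0.05 it would be 2 × 0.05 = 10% for two time points.

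**4. Success required at every time point.** Each composite's error cannot exceed 0.025, so the total cannot exceed 5%.

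**5. Power if the split is extended under *either*.** If 80% holds at 0.025, the standardised effect is 2.241 + 0.842 = 3.083, whatever the SD.
- Four tests at 0.0125 (z = 2.498): Φ(3.083 − 2.498) = 72%. Restoring 80% needs 1.173 × 527 = 618 per arm.
- Six tests at 0.0083 (z = 2.638): Φ(3.083 − 2.638) = 67%. Restoring 80% needs 1.274 × 527 = 671 per arm.

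**6. Joint power under *both* at one time point.** With 80% per test at 0.025 and composite correlation 0.5–0.7, both succeed with probability 69–71%. Without the split, each test at 0.05 has Φ(3.083 − 1.960) = 87%, and joint power is about 79–80%.

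**The case against.** The strongest reply is that no inflation has been shown. The error figures need a success rule that the documents do not state, and the synopsis wording points towards both domains, where error at two time points does not exceed 5%. Nor do the documents state an alpha, so 0.05 overall and 0.025 per test are assumptions. This stands. A reader might infer that the trial will run at a 9–13% error rate, and the documents do not support that. They leave open a rule under which it could, and others under which it would not.

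It is also fair that examining an outcome at 6 months need not mean a confirmatory test. Item IX is the only place that says when the primary objective is assessed, and it names two times. The three-time-point figures hold only on the broader reading.

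An SAP is still to be written, so part of this is unfinished specification. But the present passages disagree, and nothing in them fixes the rule before the 12-month results are read.

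On 9.1, a reader might infer that the trial is underpowered: if 527 had to be analysed, SD 26.3 with only 306 per arm would give 54% power. Section 8.3, and the statement in 9.1 that the loss was taken into account, rule that reading out.

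**Conclusion.** The concern holds as a conflict in the text with a conditional consequence. The correction covers two tests, the sections disagree on when the primary objective is tested, and no section states the success rule. Confidence in that is high.

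The size depends on the rule chosen, and all error figures rest on assumed alpha and correlations:
- *either composite, any time*: material excess over 5%, the more so if 6 months counts;
- *both composites*: none with two time points at 0.025 per test, at most 7.5% with three;
- success at every time point: none.

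The 9.1 sentence is wrong as worded, but the planned number is not shown to be too small. The 42% is labelled as loss to 12 months in 9.1, while 8.3 applies it to all study components. No separate loss to 2.5 years is given, which matters only if that time point stays primary.

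This should be fixed: it bears on the primary claim and costs little before 12-month data are seen.

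**What to change.** **Time point.** Before 12-month data are seen, reconcile the synopsis, 5.3 and 6.1 item IX by naming one confirmatory time point and making the others secondary. Twelve months matches the loss figure in 9.1. This costs wording only and leaves the planned number unchanged; the price is that the 2.5-year result becomes secondary.

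**Success rule.** State it in 9.3 and in the SAP, with the overall alpha and sidedness.
- If *either*: test PHC and MHC at half the overall alpha each.
- If *both*: no split between PHC and MHC is needed at a single time point, and joint power should be stated.

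**If more than one time point stays primary.** Under *either*, extend the split to every primary test and restate the power per test (about 72% for four, 67% for six, if 80% holds at 0.025) or the larger number required. Under *both*, divide alpha over the time points. In either case, state the loss assumed to 2.5 years and reconcile 9.1 with 8.3.

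**Section 9.1.** Write: *527 randomised per arm, about 306 per arm with 12-month data after 42% loss*. Delete the qualifier that all 527 have baseline and follow-up data, and state the SD and alpha used.
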